Briefly describe study design and anticipated enrollment, i.e., number of subjects to be enrolled by researchers study-wide and by Partners researchers. Provide a brief summary of the eligibility criteria (for example, age range, gender, medical condition). Include any local site restrictions, for example, “Enrollment at Partners will be limited to adults although the sponsor’s protocol is open to both children and adults.”

- All residents from general surgery, OMFS, urology, OB/GYN, and neurosurgery and all internal medicine first year subspecialty fellows will be enrolled in the study.
- All residents in the Association of Women’s Surgeons will be invited to participate in the study.
- Control group – 50% of the study trainee population will be randomized to control in a 1:1 manner after baseline burnout data is obtained. 50% of the coaches who volunteer will be randomized to control in a 1:1 manner after baseline burnout data is obtained. In year 3, these trainees and coaches will crossover into the coaching intervention.
- Study group – 50% of the study population will be randomized to coaching in a 1:1 manner after baseline burnout data is obtained. 50% of the coaches who volunteer will be randomized to coaching in a 1:1 manner after baseline burnout data is obtained.
- Faculty and trainees will be surveyed at beginning and end of each academic year. Surveys will be administered by a researcher not affiliated with the residency program, who has been involved in coaching research since 2011. This researcher will collect the data centrally, which will be de-identified when shared with study staff or the training programs.
- Training programs and the Association of Women Surgeons will be given access to the aggregate data, as well as the de-identified data from their training program.

Briefly describe study procedures. Include any local site restrictions, for example, “Subjects enrolled at Partners will not participate in the pharmacokinetic portion of the study.” Describe study endpoints.

- Coaches are recruited via email to all teaching faculty within the representative training programs, and volunteer their time to serve as a faculty coach. In the AWS cohort, they will be invited by email in advance of the annual meeting in October 2018. They participate in 2 hours of mandatory faculty development coach training per academic year. There is also an annual coach faculty development retreat that is not mandatory.

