- Trainees will be assigned to a professional development coach who is not likely to be a mentor, evaluator or letter-writer for the trainee
- All trainees are oriented to the coaching program during a mandatory orientation session and informed about the study. All incoming interns and fellows will be sent an email in advance to inform them of the study.
- All AWS trainees will be oriented during an informational session at the 2018 AWS Annual Meeting.
- All trainees and faculty (interventions and controls) will be asked to complete a baseline survey.
- Intervention trainees and coaches will be expected to meet quarterly to review performance and establish learning goals for subsequent rotations. There is no consequence or repercussion for not meeting.
- All trainees enrolled (interventions and controls) will be asked to complete a survey at the end of each academic year inquiring about their workplace experiences, workplace relationships, burnout, resiliency, response to stress, hardiness, happiness, and gratitude. This will serve as their baseline for the following academic year.
- All coaches (interventions and controls) will be asked to complete a survey at baseline enrollment in the program and the end of each academic year about their workplace experiences, workplace relationships, burnout, resiliency, response to stress, hardiness, happiness, and gratitude. This will serve as their baseline for the following academic year.

For studies involving treatment or diagnosis, provide information about standard of care at Partners (e.g., BWH, MGH) and indicate how the study procedures differ from standard care. Provide information on available alternative treatments, procedures, or methods of diagnosis.

This study does not involve treatment or diagnoses.

Describe how risks to subjects are minimized, for example, by using procedures which are consistent with sound research design and which do not unnecessarily expose subjects to risk or by using procedures already being performed on the subject for diagnostic or treatment purposes.

This study does not involve treatment, diagnoses, or procedures

Describe explicitly the methods for ensuring the safety of subjects. Provide objective criteria for removing a subject from the study, for example, objective criteria for worsening disease/lack of improvement and/or unacceptable adverse events. The inclusion of objective drop criteria is especially important in studies designed with placebo control groups.

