The coaching program was agreed upon by the training programs involved in this study and leadership of AWS. All trainees will be randomized but coaching program and survey participation is voluntary. In the study there is risk of discomfort for the trainees and coaches in filling out surveys about burnout and their program experience. This risk will be minimized by surveys which are de-identified and only viewed by research staff not affiliated with the training program. There will be no consequence if trainees do not complete the survey and this will be explained before completing the survey.

EXPECTED BENEFITS

Describe both the expected benefits to individual subjects participating in the research and the importance of the knowledge that may reasonably be expected to result from the study. Provide a brief, realistic summary of potential benefits to subjects, for example, "It is hoped that the

treatment will result in a partial reduction in tumor size in at least 25% of the enrolled subjects.” Indicate how the results of the study will benefit future patients with the disease/condition being studied and/or society, e.g., through increased knowledge of human physiology or behavior, improved safety, or technological advances.

All trainees participating in the Professional Development Coaching Program are expected to receive the same benefit, regardless of participation in the surveys; which is increased awareness of their accomplishments, increased opportunity for reflection, decreased burnout, improved well-being, increased resiliency, and increased opportunity to set self-directed learning goals. Additional benefits which are likely, but may be harder to capture in a survey, are increased awareness of where to turn in the event that they are struggling with work, life or professional issues.

EQUITABLE SELECTION OF SUBJECTS

The risks and benefits of the research must be fairly distributed among the populations that stand to benefit from it. No group of persons, for example, men, women, pregnant women, children, and minorities, should be categorically excluded from the research without a good scientific or ethical reason to do so. Please provide the basis for concluding that the study population is representative of the population that stands to potentially benefit from this research.

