All residents from general surgery, OMFS, urology, OB/GYN, and neurosurgery and all internal medicine first year subspecialty fellows will be enrolled in the study. All residents who are members of AWS will be invited to participate. Randomization will be carefully done to ensure gender and other demographics are balanced between groups, with the exception of the AWS cohort, which is all women, and in that cohort, we will focus on balancing the remaining demographics.

When people who do not speak English are excluded from participation in the research, provide the scientific rationale for doing so. Individuals who do not speak English should not be denied participation in research simply because it is inconvenient to translate the consent form in different languages and to have an interpreter present.

All trainees have exhibited English proficiency at the time of enrollment in the training program.

For guidance, refer to the following Partners policy:
Obtaining and Documenting Informed Consent of Subjects who do not Speak English
<http://healthcare.partners.org/phsirb/nonengco.htm>

RECRUITMENT PROCEDURES

Explain in detail the specific methodology that will be used to recruit subjects. Specifically address how, when, where and by whom subjects will be identified and approached about participation. Include any specific recruitment methods used to enhance recruitment of women and minorities.

Trainees will be asked to complete a de-identified survey in August of their training year. All trainees and faculty will be asked to complete de-identified surveys at the end of each academic year. These surveys will serve no evaluative purpose in the training program. It will be clearly described that their participation is not mandatory.

Provide details of remuneration, when applicable. Even when subjects may derive medical benefit from participation, it is often the case that extra hospital visits, meals at the hospital, parking fees or other inconveniences will result in additional out-of-pocket expenses related to study participation. Investigators may wish to consider providing reimbursement for such expenses when funding is available

None

For guidance, refer to the following Partners policies:

Recruitment of Research Subjects

<http://healthcare.partners.org/phsirb/recruit.htm>

Guidelines for Advertisements for Recruiting Subjects

<http://healthcare.partners.org/phsirb/advert.htm>

Remuneration for Research Subjects

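### Could a woman MGH surgical resident who belongs to AWS be randomised twice, once in each cohort?

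*Protocol*

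**What the plan says.** The MGH rule stands in Background and Significance, Research Design and Methods, and Equitable Selection of Subjects: "All residents from general surgery, OMFS, urology, OB/GYN, and neurosurgery and all internal medicine first year subspecialty fellows will be enrolled in the study". The AWS rule in Equitable Selection of Subjects is "All residents who are members of AWS will be invited to participate", and Research Design and Methods likewise says that AWS residents "will be invited to participate in the study". Neither rule mentions people who qualify under both.

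On allocation, Research Design and Methods states that "50% of the study trainee population will be randomized to control in a 1:1 manner after baseline burnout data is obtained", and Foreseeable Risks and Discomforts adds "All trainees will be randomized but coaching program and survey participation is voluntary". Controls move to coaching in year 3. For balancing, Equitable Selection of Subjects treats gender as relevant "with the exception of the AWS cohort, which is all women, and in that cohort, we will focus on balancing the remaining demographics".

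On timing, Recruitment Procedures says "Trainees will be asked to complete a de-identified survey in August of their training year". The study procedures say "All AWS trainees will be oriented during an informational session at the 2018 AWS Annual Meeting", and the same section places that meeting in October 2018.

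Background and Significance gives the two cohorts different coaches. At MGH the coach is a faculty member from another department; in AWS, a surgeon working in a different part of the country. It also says that a matched trainee keeps the same coach for the three years of the study.

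**The concern.** Both eligibility rules say all, and neither carves out the overlap. The AWS cohort is aimed at women surgery residents, and MGH has women in its surgical programs. The August survey followed by an October AWS orientation suggests an order: MGH allocation first, AWS recruitment second. A resident who had drawn MGH control would then have a reason to accept the AWS invitation.

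If that led to a second allocation, three things would go wrong. Some MGH controls would be coached before year 3, although Specific Aims sets the comparison against people who are not coached. Some AWS controls might already have an MGH coach. And one person could appear in both arms if the cohorts were pooled. The crossing would also be self-selected, which is the weakness of the earlier program evaluation that randomisation is meant to remove. The same question can be asked of a faculty surgeon who volunteers as a coach in both cohorts. Analysis could not fully repair any of this, because a control who has been coached cannot be made uncoached.

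**Working it through.** **Does the text lead to a second allocation?**

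1. Eligibility. The two rules overlap, and nothing gives one cohort precedence. This part of the concern is correct.
2. Allocation. The split is stated for the study trainee population as a whole. AWS members are invited to the same study in which MGH residents are already enrolled. No sentence provides for allocating an existing participant again. Separate AWS randomisation is inferred from the remark on balancing; it is not stated.
3. Control period. Controls are due to start coaching in year 3. Giving an MGH control a coach earlier through AWS would depart from the protocol.
4. Pairing. Keeping one coach for three years does not fit a second coach for a trainee already coached at MGH.
5. Timing. The August sentence names no cohort, and no sentence dates randomisation in either cohort. MGH first, then AWS is plausible but not documented.
6. Detection. One researcher collects the data centrally (Research Design and Methods), respondents enter their names (Privacy and Confidentiality), and study researchers check completeness of data and consent (Monitoring and Quality Assurance). A duplicate would be visible to that team, although no duplicate check is assigned.

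**How large would the effect be if it happened?**

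The protocol states no sample size, power, effect size or overlap count, so there is no figure of its own to reproduce. What follows is illustration.

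Two independent 1:1 allocations give each of four combinations a probability of 0.5 × 0.5 = 0.25. Discordant allocation therefore has probability 0.25 + 0.25 = 0.50, and MGH control with AWS coaching has probability 0.25.

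Let f be the share of MGH controls who are also randomised in AWS. Half of them are coached there. Assume full uptake and the full MGH effect from remote coaching, and no extra benefit from being coached twice.

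- Contrast retained: r = 1 − f/2
- Equivalent sample-size factor: 1/r²
- Power, from an assumed 80% at two-sided 0.05: Φ((1.960 + 0.842) × r − 1.960)

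| f (assumed) | MGH controls coached | r | 1/r² | Power |
|---|---|---|---|---|
| 2% | 1% | 0.99 | 1.020 | 79% |
| 5% | 2.5% | 0.975 | 1.052 | 78% |
| 10% | 5% | 0.95 | 1.108 | 76% |
| 20% | 10% | 0.90 | 1.235 | 71% |

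The upper rows need a large overlap. The denominator of f is all MGH controls, including men and first-year internal medicine fellows, neither of whom belong to the group AWS recruits here. Those who remain must also be AWS members and accept a voluntary second invitation. The documents give no basis for 10% or more, and the lower rows are at least as plausible.

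The 25% figure takes MGH-coached and MGH-control residents to join AWS equally often. If controls join more often, as the selective-crossing argument supposes, 25% no longer applies. The factor 1 − f/2 is unaffected, because f is defined among controls only.

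**The case for a change.** The strongest case for a change is that who is eligible, and how often a person is randomised, must be settled before allocation and cannot be left to the analysis plan. Even with a single randomisation, a resident who qualifies for both cohorts falls under two different coach-matching rules, and nothing says which applies. Names are collected only to link the responses of coach and trainee, so nobody is formally charged with finding duplicates. One sentence would close the gap at almost no cost.

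Much of this stands. The eligibility wording is incomplete, the point is not one for the analysis plan, and a sentence placing each trainee and coach in one cohort would do no harm. What does not stand is the step from an unstated rule to a faulty design. The text does not direct a second allocation, and its control-period and pairing rules work against one. The coach version is weaker still: coaches are invited separately for the two cohorts, and no passage has anyone serving in both. Double counting in a pooled analysis is also conjecture, since the protocol specifies no pooled analysis; it mentions only the sharing of aggregate data.

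**Conclusion.** The concern does not call for a change. The protocol leaves out which cohort a dual-eligible resident joins, a gap that study staff would fill in the obvious way: someone already enrolled and allocated at MGH stays there. Following the protocol as written does not lead to re-randomising an MGH control. Should it happen through oversight, the loss would probably be small: 1% to 5% of the MGH contrast for overlaps of 2% to 10%. Those overlaps are assumptions, and the loss would be smaller if uptake or effect in the remote cohort were less than full. The conclusion rests on reading the document as one study with one allocation per person. It would change if the cohorts were in fact randomised independently without comparing names and many MGH women surgical residents were AWS members; the protocol indicates neither.
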